6.5 Visit 5 (Follow-up period)

At 30 days following the discontinuation of treatment, enrolled patients will return for an audiometric evaluation and blood collection. If any patient develops a new decline in hearing during the 180 day follow-up period, standard corticosteroid therapy or retreatment with anakinra will be offered. The blood specimen would be used to determine the CBC with differential, SMA-7, and IL-1 β plasma level and induction. If retreatment with anakinra is indicated, a beta HCG will also be obtained (if female) before patient resumes study medication and daily symptom logs will be restarted. A 28 day dose box of anakinra will be given free of charge to the patient if retreatment is indicated during the 180 day follow up period. At that point, a letter may be sent to the patient's insurance company for possible coverage of the drug in case a sustained use of anakinra is necessary. During the 180 follow up period, the maximum number of times a patient can receive a 28 day dose of anakinra would be 4, however, we may not be able to provide this medication free of charge for this duration.

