4.4 Early Withdrawal of Subjects

4.4.1 When and How to Withdraw Subjects

Some patients may be prematurely withdrawn prior to completion of the drug for several reasons. Indications for early termination of anakinra administration is (1) Development of neutropenia as defined as an ANC of <1000, (2) Development of a serious bacterial infection (pneumonia, cellulitis, septicemia) (3) Severe injection site reaction, (4) Rash consistent with an allergic reaction to Anakinra, (5) Significant worsening of hearing threshold in either ear (greater than 20dB worsening of the pure tone average) (6) Development of renal insufficiency (as determined by a creatinine clearance of <49mL/min). The patient may also self-withdraw due to intolerance of daily injections. Although abrupt termination of drug should not pose a safety issue, a greater concern exists for hearing deterioration. If this occurs, prednisone therapy will immediately be reinstituted, barring any patient contraindications to continued corticosteroid therapy. If anakinra therapy is terminated due to safety concerns, corticosteroid therapy may be recommended, only if further hearing deterioration occurs off anakinra. Also see section 9.5: Stopping Rules. If a patient is withdrawn during study treatment, a follow-up audiogram, all safety bloods and IL-1 levels will be done approximately within 30 days of the last injection.

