6.1 Visit 1(Baseline)

Once the corticosteroid resistant patient has been identified at the end of a 28-30 day course of oral corticosteroids, enrolled patients will undergo blood testing (If the patient underwent a CBC, SMA-7 within 2 weeks prior to visit 1, those bloods will be accepted as enrollment criteria bloodwork). The audiogram taken at the end of the corticosteroid treatment will be used as the time 0 audiogram. Throughout the study, the audiologists will be blinded to the study treatment timepoint. Blood will be taken for a CBC, SMA-7, serum HCG or UCG (if female of childbearing age) and plasma IL-1 β and studies for IL-1 β stimulation in PBMC (30cc). The labs will be checked: if there is no evidence of neutropenia, renal insufficiency or pregnancy, the patient will be asked to meet with study nurses for instruction for self administration of anakinra. The patient will be asked to maintain a daily log of injections, injection site reactions and any associated symptoms (fluctuating hearing, vertigo, tinnitus, headaches).

6.2 Visit 2

At 28 days post-initial Anakinra treatment the patient will return for repeat audiometric testing and provide a blood sample (30cc). The daily logs would be reviewed by the study nurses weekly. The logs would be reviewed by the clinician at the time of the visit. Injection sites would be inspected and reactions documented. The blood specimen would be used to determine the CBC with differential, SMA-7, serum HCG (for females of child-bearing age) and IL-1 β plasma level and induction. The patient would be instructed to bring any remaining drug to the visit (if possible) as well as the spent syringes in the sharps container. The patient would be given a new 28 day supply of Anakinra and a new sharps container. CBC and SMA-7 results would be reviewed within 72 hours and any patients with changes in their white blood cell numbers, neutrophils numbers or creatinine values will be contacted. Any patient that develops neutropenia or renal insufficiency will be excluded from receiving further drug.

6.3 Visit 3

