6.8 Interval visits

Patients may ask or need (at the discretion of the investigator) to be seen at interval visits. While audiological testing is indicated, blood specimen collection (CBC w/ diff, SMA-7, beta HCG (if indicated) and IL-1 β plasma level and induction) will not be collected at these visits unless the patient is on study medication or will be resuming study medication based on the findings during the interval visit. Any patient resuming anakinra treatment during the follow-up period will be seen 28 days after the resumed medication has been started in order for the necessary blood specimens (noted above) and audiological testing to be performed. Based on that testing, the investigator may decide to either continue or stop any additional anakinra therapy.

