8.5 Stopping Rules

Patients that develop either moderate neutropenia (ANC<1000) or moderate renal insufficiency (Creatinine clearance of less than 48mL/min) will be prevented from receiving further Anakinra therapy. Allergic reaction to anakinra, severe injection site reaction, hearing deterioration of greater than 20dB PTA, or development of a serious bacterial infection will also constitute criteria for discontinuation of therapy (see section 4.4.1). The study nurses and the DSMB will be informed of these stopping rules. If greater than 25% of the total number of patients to be

recruited for this study (n=5) are prevented from completing Anakinra therapy, then the entire study will be stopped for safety concerns. Cross reference section 5.4.1.

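### Section 6.5 offers anakinra retreatment to any patient with a new hearing decline, without excepting patients stopped under 4.4.1 or 8.5 and without saying how the blood results bear on the restart

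*Protocol*

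**What the plan says.** **Retreatment.** Section 6.5 of the protocol provides that if "any patient develops a new decline in hearing during the 180 day follow-up period, standard corticosteroid therapy or retreatment with anakinra will be offered". It caps retreatment at four 28-day supplies within the 180 days and speaks of retreatment being indicated, a term it does not define. It does not refer to section 4.4.1 or 8.5.

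**Stopping.** Section 8.5 says that patients with moderate neutropenia or moderate renal insufficiency "will be prevented from receiving further Anakinra therapy". Sections 6.2 and 6.3 repeat that bar. For allergic reaction, severe injection site reaction, hearing deterioration above 20 dB PTA and serious bacterial infection, section 8.5 makes the event a criterion for discontinuing therapy and says nothing about later use. Section 4.4.1 lists the same six grounds and adds: "If anakinra therapy is terminated due to safety concerns, corticosteroid therapy may be recommended, only if further hearing deterioration occurs off anakinra".

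**Laboratory results and dosing.** At Visit 1 (section 6.1) the labs are checked and, "if there is no evidence of neutropenia, renal insufficiency or pregnancy, the patient will be asked to meet with study nurses" for injection training. In follow-up, section 6.5 says: "The blood specimen would be used to determine the CBC with differential, SMA-7, and IL-1 β plasma level and induction". It then says: "If retreatment with anakinra is indicated, a beta HCG will also be obtained (if female) before patient resumes study medication". Section 6.8 has the same bloods drawn at an interval visit when drug will be resumed, and the patient who resumes "will be seen 28 days after the resumed medication has been started" for bloods and audiometry.

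**The concern.** Two things in the retreatment text do not fit the rest of the protocol.

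First, the offer is made to every patient with a new decline. A patient taken off anakinra for toxicity, or because hearing worsened on it, falls within those words. Other sections either bar more drug for that patient or mention only corticosteroids. An investigator could follow one section and depart from another.

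Second, the first dose depends on acceptable neutrophil and renal results, while the restart text expressly places only the pregnancy test before dosing. Section 1.5 gives neutropenia and reduced renal clearance as the reasons for laboratory monitoring, so it is odd that the retreatment text leaves the role of those two results unstated.

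What is at stake is the safety of individual patients on re-exposure, and consistent conduct among the investigators who will apply these sections.

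**Working it through.** No design figure bears on this point, so the check is a comparison of sections. The only arithmetic is the exposure ceiling.

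**Step 1: exposure covered by the offer.** Inputs: at most 4 supplies of 28 days (section 6.5) and a planned course of 84 days (section 5.2). Ceiling = 4 × 28 = 112 days, and 112 / 84 = 1.33, so retreatment can exceed the main course in length. This is a maximum, not an expected exposure.

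**Step 2: the sections applied to the same patient with a new decline in follow-up.**

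- *Stopped for neutropenia or renal insufficiency.* Section 6.5: corticosteroid or anakinra. Sections 8.5, 6.2 and 6.3: no further anakinra. Section 4.4.1: corticosteroid may be recommended. All can be satisfied if the corticosteroid option is taken, but 6.5 does not say that its other option is closed.
- *Stopped for worsening above 20 dB PTA.* Section 6.5: corticosteroid or anakinra. Section 8.5: therapy discontinued, with no word on later use. Section 4.4.1: corticosteroid only. This is the plainest case. The drug was stopped because hearing worsened, and a further decline is the very event that triggers the offer of the same drug.
- *Stopped for allergic reaction, severe injection site reaction or serious bacterial infection.* The texts stand as in the second case.
- *Completed 84 days with no stopping criterion.* No conflict about the offer. Sections 6.5 and 6.8 do not say whether 4.4.1 and 8.5 apply during the retreatment itself.

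The explicit bar on further drug therefore covers two of the six grounds. For the other four, the answer depends on whether the reader follows 6.5 or 4.4.1.

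**Step 3: how results are linked to dosing.**

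- *Visit 1 (6.1):* bloods drawn and results checked; dosing depends on them.
- *Visits 2 and 3 (6.2, 6.3):* the next box is handed over at the visit; results are reviewed within 72 hours; neutropenia or renal insufficiency excludes the patient from more drug.
- *Restart in follow-up (6.5, 6.8):* CBC and SMA-7 drawn; pregnancy test expressly before resumption; no stated link between the neutrophil or renal result and the first restart.
- *28 days after restart (6.8):* bloods and audiometry repeated; on that testing the investigator may continue or stop.

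So the tests are in place, and continuation beyond the first retreatment box is tied to them. The unstated step is how the restart-visit results bear on the first retreatment box.

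**The case against.** The best defence is that the sections can be read together. Section 8.5 sets no time limit on its bar, and a specific prohibition would ordinarily limit a general offer. The offer in 6.5 is an alternative, with corticosteroids as one branch, and retreatment has to be indicated. Section 4.4.1 also gives withdrawn patients their own follow-up, an audiogram and bloods within about 30 days of the last injection, so they may never enter the 180-day period.

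This has force for neutropenia and renal insufficiency, where the conflict is one of wording that a careful reader could resolve. It does not settle the other four grounds, for which 8.5 does not bar later use. Nor does it define when retreatment is indicated. Section 6.5 counts from the end of treatment and speaks of enrolled patients, while 4.4.1 concerns ending drug administration and itself foresees decline off drug. If withdrawn patients are meant to be outside 6.5, no section says so.

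Three stronger readings are tempting, and the protocol does not support them.

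- *That drug is restarted with no neutrophil or renal test, or on results from an earlier scheduled visit.* CBC and SMA-7 are drawn at Visits 5 to 7 and at any interval visit where drug will resume. Only the link from result to restart is unstated.
- *That late retreatment escapes monitoring because Visit 7 ends the study.* Section 6.8 runs the 28-day check from the restart, and section 8.1 runs adverse event reporting to 30 days after the last study treatment.
- *That the secondary safety objective is compromised.* Section 2 defines it for a three month course and section 7.2 for 84 consecutive days; retreatment lies outside both.

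**Conclusion.** The point holds as an unreconciled conflict between sections, together with one unstated link. As written, 6.5 allows anakinra to be offered again, for up to 112 days, to a patient stopped under 4.4.1 or 8.5. For four of the six stopping grounds no other section expressly forbids it, while 4.4.1 names corticosteroids alone. The missing link between the restart bloods and the first retreatment box is a lesser matter, since the bloods are already drawn.

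This rests on reading the offer in 6.5 literally and on patients stopped for safety being within the follow-up it governs. The protocol neither confirms nor excludes the second assumption. It gives no basis for estimating how many patients would be affected. The correction is worth making because it concerns re-exposure after a safety stop and costs very little.

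**What to change.** The sponsor should reconcile sections 6.5 and 6.8 with 4.4.1, 6.1 and 8.5 (and with the matching sentences in 6.2 and 6.3), so that every section gives the same answer on three matters:

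1. how a patient who met a stopping criterion is handled when hearing declines in follow-up, including whether such a patient is within 6.5 at all;
2. whether 4.4.1 and 8.5 apply during retreatment;
3. how the CBC and SMA-7 already drawn when drug is to be resumed bear on the restart.

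Which clinical rule is right is for the sponsor to decide, and none is proposed here. The cost is an amendment to wording, with the review by the ethics committee or IRB that section 11 requires. Reconciling the text does not in itself call for a new test or visit.

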6.6 Visit 6 (Follow up period)

At 90 days following the discontinuation of treatment, enrolled patients will return for an audiometric evaluation and blood collection. The blood specimen would be used to determine the CBC with differential, SMA-7, and IL-1 β plasma level and induction.

CONFIDENTIAL This material is the property of the Feinstein Institute for Medical Research, North-Shore-LIJ Health System. Do not disclose or use except as authorized in writing by the study sponsor

6.7 Visit 7(End of study)

At 180 days following the discontinuation of treatment, enrolled patients will return for an audiometric evaluation and blood collection. The blood specimen would be used to determine the CBC with differential, SMA-7, and IL-1 β plasma level and induction.

6.8 Interval visits

Patients may ask or need (at the discretion of the investigator) to be seen at interval visits. While audiological testing is indicated, blood specimen collection (CBC w/ diff, SMA-7, beta HCG (if indicated) and IL-1 β plasma level and induction) will not be collected at these visits unless the patient is on study medication or will be resuming study medication based on the findings during the interval visit. Any patient resuming anakinra treatment during the follow-up period will be seen 28 days after the resumed medication has been started in order for the necessary blood specimens (noted above) and audiological testing to be performed. Based on that testing, the investigator may decide to either continue or stop any additional anakinra therapy.

6.9 Research Blood Sample Collection and Storage

The plasma for IL-1 β and IL-1 β stimulation (30 cc) will be transported by hand by the P.I. to FIMR, where it will be stored at -20C in a locked freezer until further testing is performed. The sample number corresponds to the patient ID number assigned at enrollment. Second number is assigned in a database that corresponds to both the patient ID number and the date the sample was acquired. This information is a password protected database, accessible only by research laboratory assistant.

7 Statistical Plan

7.1 Sample Size Determination & Statistical Methods

Corticosteroid resistant AIED patients currently have no therapeutic alternatives available to them. These patients that failed initial corticosteroid therapy are not expected to demonstrate a placebo effect, as they have already undergone 2 serial audiograms that demonstrated a <5dB PTA improvement in hearing for trial inclusion. A Simon 2-stage "optimal" design will be used to test the null hypothesis that the true objective response rate (RR) is 10% or less (which would not be clinically meaningful) versus the alternative hypothesis that the true response rate is 30% or greater. With a significance level of 0.05 and a power of 0.80, a maximum total of 29 evaluable patients will be required to assess the objective response rate. Ten (10) evaluable patients will be enrolled in Stage 1(R21 phase). If 1 or fewer objective responses are observed in the first 10 evaluable patients, then the trial will be terminated (do not proceed to R33). Primary milestone: If 2 or more objective responses (improvement in the PTA \geq 5dB) are observed in the first 10 patients (20%), we will proceed to the R33 phase.

If the RR is 10% or less, then the expected sample size for the trial is 15 patients and the probability of early termination at the end of the R21 phase (stage 1) is 74%. Overall, a total of approximately 38 patients may be enrolled in this R21/R33 study to ensure that the specified numbers of evaluable patients are available for analysis at each stage.

Given that anakinra may cause injection site reactions, it is possible that some patients will prematurely self-terminate the study. In order to appropriately evaluate the results, 29 patients would need to complete the 84-day course of anakinra. Overall, a total of 38 patients may be enrolled in this study to ensure that the specified numbers of evaluable patients are available for analysis at each stage.

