3.1 General Design

- The proposed study will be a Phase I/II, single-centered, open-label trial of Anakinra in corticosteroid resistant patients with AIED.
- Trial design:

Patient & Audiometric Criteria: All patients to be included in this phase I/II clinical trial must exhibit development of sensorineural hearing loss (SNHL) of greater than 30dB at one or more frequencies in *both* ears with evidence of active deterioration (elevated threshold) in at least one ear of 15 dB at one frequency (excluding 250 or 8kHz as a sole indicator), or 10dB at 2+ frequencies developing in >3 days but <90 days (7). If after the first 10 subjects are recruited, no untoward effect on hearing is identified, subjects with unilateral hearing loss may also be included. To utilize the expanded criteria defined above, progressive sensorineural hearing loss potentially attributed to anakinra therapy cannot be observed in the first 10 evaluable patients. If progressive SNHL is observed in over 25% but less than 50% of patients receiving anakinra during the initial phase, we would NOT utilize the expanded criteria.

- This group of potential patients may include those patients previously diagnosed as sudden SNHL if they demonstrated features suspicious for of autoimmune disease (if they have a systemic autoimmune disorder, family history of autoimmune disease, or if they had previous episodes of sudden sensorineural hearing loss in the same or contralateral ear), as long as they meet the audiologic criteria defined above with the exception that the hearing loss may evolve in less than 3 days. Similarly, patients previously diagnosed as Meniere's Disease with autoimmune features may be included if they meet the audiologic criteria as defined above. Patients were excluded from study if they had evidence of retrocochlear pathology on their MRI scan.

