4.4.2 Data Collection and Follow-up for Withdrawn Subjects

Even if patients prematurely withdraw, or are withdrawn from the study, an analysis of all data collected through the time of withdrawal will be included for analysis. Data on the withdrawn

CONFIDENTIAL This material is the property of the Feinstein Institute for Medical Research, North-Shore-LIJ Health System. Do not disclose or use except as authorized in writing by the study sponsor subjects is critical to the integrity of the final data analysis, especially for safety and tolerability issues.

5 Study Drug

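### The study-wide safety stop in section 8.5 gives two triggers that do not agree: more than 25% of the 38 patients to be recruited is 10, but 5 is printed

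*Protocol*

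**What the plan says.** **The study stop.** Section 8.5 lists the reasons for ending a patient's treatment: neutropenia, renal insufficiency, allergic reaction, severe injection site reaction, serious bacterial infection and hearing loss. It then gives one rule for the whole study, in a sentence split by a page break. The percentage stands before the break: "If greater than 25% of the total number of patients to be". The count and the consequence stand after it: "recruited for this study (n=5) are prevented from completing Anakinra therapy, then the entire study will be stopped for safety concerns".

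**Number to be recruited.** The Study Summary gives 38 subjects. Section 7.1 also gives 38, so that enough evaluable patients are available: "29 patients would need to complete the 84-day course of anakinra".

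**Hearing loss in the stop.** Section 8.5 sets the level: "hearing deterioration of greater than 20dB PTA, or development of a serious bacterial infection will also constitute criteria for discontinuation of therapy". Section 4.4.1 has the same threshold, judged per ear: "Significant worsening of hearing threshold in either ear (greater than 20dB worsening of the pure tone average").

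**Hearing loss in the first 10 patients.** Section 3.1 allows enrolment of unilateral cases only if no progressive loss potentially due to anakinra is seen in the first 10 evaluable patients. It then adds a band: "If progressive SNHL is observed in over 25% but less than 50% of patients receiving anakinra during the initial phase", the expanded criteria are not used. It says nothing for 50% or more.

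**Stage 2 gate.** Under section 7.1, 1 or fewer responses in 10 ends the trial. If 2 or more "are observed in the first 10 patients (20%), we will proceed to the R33 phase".

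**The concern.** A stopping rule has to yield one number. This one gives a percentage and a count that do not match for the enrolment in the same protocol, and section 8.5 says that the study nurses and the DSMB will be told of it. One person could halt the study at the fifth discontinuation and another could wait for the tenth, each following the text.

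The choice also decides how much section 8.5 can do early on. With 10 patients treated, a trigger of 5 can end the study within Stage 1. A trigger of 10 would need every one of them to be discontinued.

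The gap in section 3.1 is related but smaller. The upper limit of 50% suggests that something different follows above it, yet no action for the study is stated. Section 8.5 fills this only in part, because losses of 20 dB PTA or less do not enter the stop as a hearing criterion. Worsening hearing is a listed safety endpoint (section 3.3) and a stated risk (section 11.2).

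**Working it through.** **1. The plan's own design figures (section 7.1).** Inputs: 10 patients in Stage 1, stop at 1 or fewer responses, 29 in total, null response rate 10%.

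- Early termination under the null: 0.9^10 + 10 × 0.1 × 0.9^9 = 0.349 + 0.387 = 0.736, stated as 74%.
- Expected size: 10 + (1 − 0.736) × 19 = 15.0, stated as 15.

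A search for the optimal Simon design (10% versus 30%, alpha 0.05, power 0.80) returns the same 10 and 29, with alpha 0.047 and power 0.805. The sample size is sound; the fault lies in the safety rule.

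**2. The trigger in section 8.5.** More than 25% means the smallest whole number above 0.25 × N.

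- N = 38 to be recruited: 0.25 × 38 = 9.5, so 10 patients (10/38 = 26.3%).
- N = 29 evaluable: 0.25 × 29 = 7.25, so 8 patients.
- N = 10 in Stage 1: 0.25 × 10 = 2.5, so 3 patients.
- The printed 5 is 5/38 = 13.2% or 5/29 = 17.2%. It is the first count above 25% only for N from 16 to 19, and exactly 25% of 20.

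None of the totals 38, 29 or 10 gives 5.

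**3. What the choice does.** Let X be the number discontinued among 38, taken as Binomial(38, q). The protocol gives no q, so a range is shown.

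| Assumed q | P(X ≥ 5) | P(X ≥ 10) |
|---|---|---|
| 5% | 0.04 | under 0.001 |
| 10% | 0.33 | 0.003 |
| 15% | 0.69 | 0.05 |
| 20% | 0.90 | 0.22 |
| 25% | 0.98 | 0.49 |

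**4. Self-withdrawals.** Section 7.1 expects some patients to stop by themselves and allows for 38 − 29 = 9 non-completers (9/38 = 23.7%). Section 8.5 does not say whether these count. If they do, the planned allowance already exceeds a trigger of 5: at q = 23.7% the stop is reached with probability 0.96 at 5 patients and 0.41 at 10.

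**5. Hearing loss side by side.** Section 3.1 concerns who may be enrolled, and its band ends below 50%. Section 8.5 concerns stopping and counts hearing only above 20 dB PTA. Section 7.1 concerns responses only. None states a study-level action for progressive loss of 20 dB or less, at any frequency.

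**6. False pauses if a review is set at 5 or more of 10.** If 10%, 20%, 30% or 40% of patients worsen past the chosen threshold through their disease alone (assumed), the binomial chance of 5 or more in 10 is 0.002, 0.033, 0.150 or 0.367.

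**The case against.** The strongest reply is that the trial is well guarded apart from one misprint, and much of that stands.

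- **Stage 2 without a safety brake.** A reader might infer from the gate in section 7.1 that Stage 2 opens unprotected. The protocol does not support this. Response rules and safety rules are usually separate layers, and section 8.5 stays in force when Stage 2 opens. The DSMB meets every 6 months, has direct access to the audiometric data and may review both safety and efficacy (section 8.6.1). Audiograms are taken every 28 days on treatment, and section 11.2 lets patient or physician discontinue if the disease worsens significantly. What is absent is only a review tied to the Stage 1 decision.
- **A stop at 10 as useless.** A reader might argue that a tenth loss leaves 28 of the 29 completers needed, so a stop at 10 protects nobody. That confuses two things. Missing 29 completers weakens the efficacy test but halts no dosing; section 8.5 does halt it. At an assumed 25% discontinuation, a stop at 10 is reached with probability 0.49.
- **Section 3.1 is an eligibility rule.** Its preceding sentence already bars expansion after any attributable progressive loss in the first 10, so 50% or more is covered for that purpose. The gap is only in what happens to the study.
- **Natural progression.** Patients are selected for active deterioration and there is no control group, so worsening need not be due to the drug. This argues for review rather than an automatic stop.

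None of these replies reconciles 25% of 38 with 5.

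**Conclusion.** Section 8.5 is wrong as written. Its percentage and its count differ by a factor of two for the stated enrolment of 38 (10 against 5), and no total in the design gives 5. At assumed discontinuation rates of 10% to 20%, the chance of stopping is 0.33 to 0.90 under one reading and 0.003 to 0.22 under the other. These figures assume that all 38 are enrolled, a common rate and independent patients; a trial that ends for futility in Stage 1 would reach either count less often. The contradiction itself rests on no assumption.

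The missing action at 50% or more in section 3.1 is a real but secondary gap. Any probability that Stage 2 opens after widespread worsening would rest on worsening rates that the protocol does not give, so none is offered as a finding. The response-only gate in section 7.1 is not an error.

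**What to change.** **Needed, section 8.5.** State one count with its denominator, confirmed with the DSMB, and delete or correct the other figure. Say whether self-withdrawals count. The protocol does not show which number was meant. Five is the more protective choice, and its cost is the first column of the table: the study would be stopped with probability 0.33, 0.69 or 0.90 if 10%, 15% or 20% of patients were discontinued. If self-withdrawals count, 5 also conflicts with the allowance of 9 non-completers in section 7.1.

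**Secondary, sections 3.1 and 8.5.** State that progressive hearing loss attributable to anakinra in 50% or more of Stage 1 patients triggers review by the existing DSMB before Stage 2 accrual, with the PTA threshold set by the DSMB. Withdrawn patients can be included, since section 4.4.2 says "an analysis of all data collected through the time of withdrawal will be included for analysis".

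**Cost.** A few lines of text and at most one extra call of a board that already holds the data. The downside is a possible short pause caused by natural progression, with the chances in step 6 of the working; counting only attributable losses should lower them. The Stage 1 response rule and the sample size need no change.
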